5. JUSTIFICATION

I) Summary of Relevant Non-Clinical and Clinical Findings for the Current Study

Ulcerative colitis (UC) is a chronic inflammatory bowel disease of unknown cause, characterized by flares or periods of active disease alternating with periods of remission or inactivity. Treatment is primarily based on the use of salicylic acid derivatives,

corticosteroids, immunosuppressants, anti-TNF antibodies, and anti-integrin antibodies. The management of flares depends on both the extent of the disease and the severity of symptoms. It is well-established that mild flares are treated with aminosalicylates, while severe flares require hospitalization and intensive treatment with intravenous corticosteroids. According to recommendations from the European Crohn's and Colitis Organization (ECCO), the treatment for moderate UC flares should also rely on aminosalicylates, with oral corticosteroids used as rescue therapy when there is no improvement with aminosalicylates. However, in clinical practice, many of these patients already receive maintenance therapy with aminosalicylates (often at high doses), making oral corticosteroids the initial treatment option in most cases. Nonetheless, the efficacy of oral corticosteroids for moderate flares has been scarcely evaluated, with reported success rates between 30% and 50% in limited randomized controlled trials (2-5).

In clinical practice, intravenous corticosteroids are frequently used for moderate flares. There is evidence suggesting that intravenous administration may have greater efficacy in moderate UC activity. A retrospective study conducted in our setting showed that in UC patients who responded to an initial course of corticosteroids, intravenous administration during moderate flares was associated with a lower relapse rate (61% compared to 80%, $p=0.027$) (6). This high relapse and/or corticosteroid dependency rate may be related to achieving clinical remission without endoscopic remission (7).

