7. STUDY DESIGN

I) Primary and Secondary Variables

Primary Outcome Variable:

Clinical and endoscopic remission, steroid-free at 8 and 54 weeks, without rescue treatment and without the need for steroids up to week 54.

Secondary Variables (Variables of Interest):

- **Clinical Remission** (assessed at weeks 8 and 54): Mayo Score \leq 2 points with no individual variable $>$ 1.
- **Endoscopic Remission**: Mayo endoscopic subscore of 0 or 1.
- **Clinical Response** (assessed at weeks 8 and 54): a reduction in the Mayo score by at least 3 points and at least 30%, with a decrease in the rectal bleeding subscore of at least 1 point or to an absolute value of 0 or 1.
- **Early Clinical Response**: a decrease in the clinical Mayo subscore by at least 3 points and at least 30%, with a decrease in the rectal bleeding subscore of at least 1 point or to an absolute value of 0 or 1, at days 3 and 7 of corticosteroid treatment.
- **Relapse**: reappearance of symptoms, defined as a Mayo clinical subscore $>$ 2. The time of relapse from treatment initiation will be recorded.
- **Corticosteroid Dependency**: relapse during prednisone tapering or within three months after corticosteroid discontinuation.
- **Rescue Treatment**: restart or increase of the established corticosteroid dose (including topically acting oral corticosteroids) or initiation of any treatment for ulcerative colitis other than mesalazine, including biological agents (infliximab, adalimumab, golimumab, vedolizumab), calcineurin inhibitors (cyclosporine, tacrolimus), thiopurines (azathioprine, mercaptopurine), methotrexate, leukapheresis, or colectomy.
- **Need for Surgery** and time to surgery from treatment initiation.
- **Adverse Event Rate** and rate of severe adverse events (including hospitalizations) recorded throughout the study duration.
- **Fecal Calprotectin Determination**.

II) Study Design

This is a Phase IV, controlled, prospective, randomized, open, multicenter study to compare two corticosteroid treatment regimens for moderate UC flares.

III) Estimated Number of Subjects, Sample Size, and Justification

Study Subjects: Adult patients of both sexes with active moderate ulcerative colitis, with or without maintenance treatment or with oral/topical mesalazine.

Sample Size: 148 patients.

Sample Size Calculation:

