- **Probable:** There is a reasonable temporal sequence between the administration of the drug and the occurrence of the AE. This event matches the ARs described for the drug, improves after treatment is interrupted, and cannot be explained by other alternatives.
- **Possible:** There is a reasonable temporal sequence between the administration of the drug and the occurrence of the AE. This event matches the ARs described for the drug but may be explained by alternative causes.
- **Conditional or Unlikely:** There is a reasonable temporal sequence between the administration of the drug and the occurrence of the AE. This event does not match the ARs described for the drug and may be explained by alternative causes.
- **Unrelated:** There is no reasonable temporal sequence between the administration of the drug and the occurrence of the AE. This event does not match the ARs described for the drug and may be explained by alternative causes.

For expeditious reporting, the categories "definitive," "probable," and "possible" from the Karch and Lasagna (1977) algorithm will be considered related, and the category "conditional or unlikely" will be considered unrelated.

Determining the potential relationship to the study treatment is the responsibility of the principal investigator at the research site or the person designated by them.

Serious Adverse Event (SAE)

Any harmful incident affecting the health of a subject that, at any dose:

- Requires hospitalization or prolongation of hospitalization,
- Causes permanent or significant disability or incapacity,
- Leads to a congenital anomaly or malformation,
- Poses a threat to life or results in death,
- Is considered medically significant.

For reporting purposes, any suspected AE or AR deemed medically important will also be treated as serious, even if they do not meet the previous criteria, including medical events requiring intervention to prevent any of the aforementioned outcomes. Any suspected transmission of an infectious agent via a medication will also be considered serious.

The term "life-threatening" refers to the investigator's opinion that the patient is at real risk of death at the time of the AE or AR; it does not refer to the hypothetical possibility that the AE/AR could have led to death if it had been more severe.

It should not be confused with the term "severe," which refers to the intensity of the AE or AR (mild/moderate/severe).

Serious and Unexpected Adverse Reaction (SUSAR)

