A serious adverse reaction whose nature, severity, or outcome is inconsistent with the reference safety information. In this case, the product information (SmPC) will be used as the reference.

SAEs that meet the SUSAR criteria and are associated with blinded studies should be reported to Health Authorities with the open-label unblinding.

Adverse Events of Special Interest in this Study

Infections, events that lead to the discontinuation of the study treatment, and the development of diabetes mellitus or hypertension are considered of special interest.

Expected Adverse Reactions Not Clinically Significant in this Study

The following adverse reactions are commonly associated with the study medication in clinical practice. They will be recorded in the patient's medical history, but for reporting purposes, they will not be collected in the e-CRF unless, in the investigator's clinical judgment, they meet the severity criteria.

These include the occurrence of hirsutism, moon face, acne, insomnia, weight gain, buffalo hump, and stretch marks.

II) Methods and Schedule for Evaluation, Recording, and Analysis of Safety Parameters

Adverse events will be recorded from the administration of the study drug until the end of the patient's participation in the study, whether spontaneously reported by the patient or detected during study visits.

Follow-up of all ARs, SAEs, and SAREs will be conducted until resolution, irreversibility, or study completion, whichever occurs first.

All ARs, SAEs, SAREs must be documented in the patient's medical history and in the e-CRF, except for clinically insignificant ARs described above.

Any pregnancy occurring during the study and its outcome must be recorded and followed to rule out congenital anomalies or malformations. Information will be gathered on:

- Normal birth, spontaneous or therapeutic abortion (any congenital anomaly detected in the aborted fetus should be documented), stillbirth, congenital anomaly.
- Neonatal deaths within 30 days of birth.
- Infant death after 30 days if the investigator suspects it is related to in-utero exposure to the study medication.
- All infants born after fetal exposure must be followed during the first 12 months after delivery.

Any exacerbation of a pre-existing disease occurring after the start of the study treatment is also considered an adverse event.

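### Colitis worsening and colitis admissions can enter the adverse-event comparison and, if the bolus is more effective, could mask a steroid-toxicity excess; show the comparison with and without them

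*Combined protocol and SAP*

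**What the plan says.** Section 11.II (protocol) states: "Any exacerbation of a pre-existing disease occurring after the start of the study treatment is also considered an adverse event". Ulcerative colitis is an inclusion criterion (section 8.I), so it is a pre-existing disease in every participant. The sentence neither names nor excludes it.

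Section 11.I makes an event serious if it "Requires hospitalization or prolongation of hospitalization", with no exception for colitis admissions. Section 7.I lists the adverse-event rate as a secondary variable, together with the "rate of severe adverse events (including hospitalizations) recorded throughout the study duration". Section 11.I treats seriousness and severity as different concepts: "It should not be confused with the term 'severe,' which refers to the intensity of the AE or AR (mild/moderate/severe". Section 7.I nevertheless files hospitalizations under severe.

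The same clinical events are also outcomes elsewhere. Section 7.I defines relapse as "reappearance of symptoms, defined as a Mayo clinical subscore" above 2, counts colectomy as rescue treatment and lists need for surgery. Sections 3 and 6 make need for hospitalization a secondary objective.

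On recording, section 11.II says "All ARs, SAEs, SAREs must be documented in the patient's medical history and in the e-CRF". Section 11.I takes seven familiar steroid effects (acne, moon face and insomnia among them) and says "they will not be collected in the e-CRF unless, in the investigator's clinical judgment, they meet the severity criteria".

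Section 12 gives chi-squared and t-tests for most secondary objectives. It specifies no safety analysis by relatedness, by special-interest category, or with colitis events set apart.

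**The concern.** The safety question is whether adding three methylprednisolone boluses causes extra harm. Section 5.II anticipates that bolus treatment can be given to outpatients without a higher risk of adverse events, so the between-arm safety rates will be read as the test of that expectation.

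The trial is designed on the premise that treatment failure is common and unequal: 80% in the oral arm and 60% in the bolus arm. Any failures recorded as adverse events add more to the oral arm's count than to the bolus arm's, which works against detecting a toxicity excess in the bolus arm. Leaving common steroid effects out of the e-CRF removes some drug toxicity from the count while colitis worsening can stay in it.

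**Working it through.** **Inputs from the documents.** Primary success is 20% with oral treatment (section 7.III) and 40% with the bolus (section 12, interim analysis), so failure is 80% and 60%. Allocation is 1:1 of 148, or 74 per arm.

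**Check of the plan's own figure.** The documents give no expected adverse-event rate. The only stated figure that rests on these success rates is the sample size. For 20% v 40%, one-sided 0.05, 80% power, pooled variance: 64 per arm; 64/0.90 = 71.1, rounded up to 72; total 144. That is within 3% of 148, so 80% v 60% failure is a fair reading of the design.

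**Assumed inputs, not in the documents.** *f* is the share of primary failures recorded as a colitis adverse event. *t* is the rate of non-colitis adverse events. The two are taken as independent within arm.

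**Formula.** P(any adverse event) = 1 - (1 - f × failure)(1 - t).

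**Any adverse event, t = 20% oral and 40% bolus (true excess +20 points).** Power is for two-sided 0.05 at 74 per arm.

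| f | Oral | Bolus | Difference | Power |
|---|---|---|---|---|
| 0 | 20.0% | 40.0% | +20.0 | 0.76 |
| 0.25 | 1 - 0.80 × 0.80 = 36.0% | 1 - 0.85 × 0.60 = 49.0% | +13.0 | 0.36 |
| 0.50 | 1 - 0.60 × 0.80 = 52.0% | 1 - 0.70 × 0.60 = 58.0% | +6.0 | 0.11 |
| 0.75 | 1 - 0.40 × 0.80 = 68.0% | 1 - 0.55 × 0.60 = 67.0% | -1.0 | reversed |
| 1 | 1 - 0.20 × 0.80 = 84.0% | 1 - 0.40 × 0.60 = 76.0% | -8.0 | reversed |

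**Excess that would be cancelled exactly.** Setting the two arms equal with t = 20% in the oral arm gives a hidden excess of 4.7 points at f = 0.25, 11.4 at 0.50, 21.8 at 0.75 and 40 at 1.

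**Equal efficacy (80% failure in both arms, same t).** At f = 0.50: 52.0% v 1 - 0.60 × 0.60 = 64.0%, or +12. At f = 1: 84.0% v 1 - 0.20 × 0.60 = 88.0%, or +4. The excess shrinks but keeps its sign.

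**Serious events.** Assume non-colitis serious rates of 3% oral and 6% bolus (true +3.0 points), and let *a* be the share of failures admitted for colitis.

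| a | Oral | Bolus | Difference |
|---|---|---|---|
| 0.05 | 1 - 0.96 × 0.97 = 6.9% | 1 - 0.97 × 0.94 = 8.8% | +1.9 |
| 0.10 | 1 - 0.92 × 0.97 = 10.8% | 1 - 0.94 × 0.94 = 11.6% | +0.9 |
| 0.15 | 1 - 0.88 × 0.97 = 14.6% | 1 - 0.91 × 0.94 = 14.5% | -0.2 |
| 0.20 | 1 - 0.84 × 0.97 = 18.5% | 1 - 0.88 × 0.94 = 17.3% | -1.2 |

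**Alternative input: relapse in place of f × failure.** Section 5.I cites relapse of 61% (intravenous) and 80% (oral). With assumed t of 40% bolus and 25% oral (true +15): 1 - 0.39 × 0.60 = 76.6% v 1 - 0.20 × 0.75 = 85.0%, or -8.4. With assumed relapse of 40% v 50%: 64.0% v 62.5%, or +1.5. With 30% in both arms: 58.0% v 47.5%, or +10.5. The sign depends on the inputs.

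**The case against.** The strongest case against is that the text does not settle whether ordinary flares count. The pre-existing-disease sentence can be read as covering comorbidities. Section 12 distinguishes non-completion through adverse events from non-completion through treatment failure, and section 8.III lists steroid complications separately from clinical worsening. The explicit e-CRF requirement names adverse reactions and serious events, so a non-serious flare judged unrelated to treatment might never be entered. This stands for non-serious flares, although section 11.II also says that adverse events will be recorded and section 7.I needs a rate of them. It does not reach admissions, which meet the seriousness criterion and sit inside the severe-event rate.

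Second, the data to isolate toxicity are collected: events are classified for causality, and infections, new diabetes and new hypertension are of special interest (section 11.I). That is true, but no comparison using them is planned. The related/unrelated grouping is stated for expedited reporting, and the special-interest item on events leading to discontinuation could itself capture treatment failure.

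Third, an opposing bias exists. Failures may be withdrawn (sections 7.VII and 8.III) and recording ends with participation (section 11.II), so the arm with more failures may have less time in which to report events. The net direction is therefore not fixed.

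Fourth, an all-cause count is a legitimate safety table, and deciding which events are colitis falls to open-label investigators. This is a good reason not to replace the all-events comparison.

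A reader might also infer that the safety endpoint largely re-measures efficacy, or that an ineffective bolus would look toxic. The documents support neither. The colitis share depends on *f* and on the toxicity and admission rates, which are not given, and a primary failure such as endoscopic non-remission need not be an exacerbation. With equal efficacy the excess is diluted, as shown above; false toxicity would need more relapse on the bolus than on oral treatment. Nor does the reversal at 61% v 80% predict this trial: those figures are retrospective, come from initial responders and carry no stated time horizon.

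**Conclusion.** The point holds as an ambiguity with a plausible cost. As written, colitis worsening can count as an adverse event, colitis admissions do enter the severe/serious rate, and no planned analysis separates them from drug harm. If the bolus is more effective, this can mask a toxicity excess. At the design failure rates and the assumed toxicity rates, reversal appears only when about three quarters of failures are recorded as colitis events, or about 15% of failures are admitted. If efficacy is equal, there is dilution only.

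The true size cannot be derived from the documents, because *f*, *a* and the toxicity rates are all assumptions, as is independence between toxicity and failure. Shorter observation of withdrawn failures may push the other way. The change is worth making because it is cheap and makes the safety comparison interpretable, not because a bias of known size has been shown.

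**What to change.** In sections 7.I, 11.II and 12, pre-specify that:

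- the between-arm adverse-event and serious-event comparisons are each shown twice, for all events and excluding worsening of ulcerative colitis and admission or surgery for it;
- colitis events are tabulated separately by arm;
- treatment-related events and the listed events of special interest are also compared between arms, from data already collected.

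State in section 11.II whether non-serious colitis flares are entered in the e-CRF as adverse events. Reconcile severe in section 7.I with serious in section 11.I, so that it is clear which rate hospitalizations belong to. Leave individual safety reporting unchanged.

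The cost is a sentence in each section and one event flag, with no added patients, visits or samples. The downside is that open-label investigators assign the flag, which is why the all-events table stays beside the restricted one.

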Corticosteroid bolus therapy consists of administering supraphysiological doses of corticosteroids over a short period (2 to 5 days) without a subsequent tapering schedule. This therapeutic approach has been associated with a prolonged therapeutic effect without the feared adverse effects typically seen with corticosteroid therapy. In UC, four studies have reported results on corticosteroid boluses (two of which were retrospective studies in pediatric patients, one in severe UC, and one in moderate UC). These studies, with limited patient numbers and varying regimens (mainly involving oral corticosteroids after the initial boluses), suggested a faster therapeutic effect without an increase in adverse effects (13-16). This strategy may allow for outpatient intravenous corticosteroid administration, avoiding hospital admissions typically required in clinical practice, without increasing the risk of adverse events.

Treatment Groups:

1. **Intravenous Bolus Group:** 0.5 g/day of methylprednisolone for 3 consecutive days, followed by oral prednisone at 60 mg/day for one week, then a tapering regimen (decrease by 10 mg weekly until a dose of 20 mg, followed by a decrease of 5 mg weekly until complete withdrawal).
2. **Oral Prednisone Group:** 60 mg/day for one week, followed by a tapering regimen (decrease by 10 mg weekly until a dose of 20 mg, followed by a decrease of 5 mg weekly until complete withdrawal).

In both groups:

- Concomitant treatment with 1g/day 5-ASA suppositories during the first four weeks.
- Concomitant treatment with calcium (1000 mg/day) and vitamin D (800 IU/day) until corticosteroids are withdrawn.
- Maintenance treatment with mesalazine 2-2.4 g/day starting from the reduction to 20 mg/day of prednisone (for patients on 5-ASA at the time of flare-up, this will be stopped at study inclusion).
- Any other concomitant treatment the patient receives during the study must be documented in the e-CRD.

III) General and Specific Guidelines for Investigators

Investigators must strictly adhere to the protocol and completely fill out the electronic data collection form (e-CRD) provided by the sponsor.

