The trial will be conducted in accordance with the recommendations for clinical trials and the evaluation of drugs in humans, as outlined in the Declaration of Helsinki (1964), and its revisions in Tokyo, Venice, Hong Kong, South Africa, Edinburgh, Washington, Tokyo, and Seoul (2008), Good Clinical Practice (GCP) standards, and current Spanish legislation (Royal Decree 1090/2015) on clinical trials.

If any participant experiences a disease or adverse event that requires pharmacological treatment or modifies the study drugs' disposition, the study medication must be withdrawn. In such cases, the adverse event will be monitored until resolution and the participant followed up until the end of the study. If the adverse reaction is mild or moderate and does not require suspension of the drug, it will be documented, and the study will continue as planned.

IV) Study Population Description

A total of 148 patients with moderate activity ulcerative colitis, without maintenance treatment or with oral/topical mesalazine, will be stratified based on disease onset and maintenance treatment with mesalazine at doses >2g/day in the last three months and randomized 1:1 into two treatment arms.

V) Literature References and Relevant Data

Recommendations of the European Crohn's and Colitis Organization governing clinical practice in ulcerative colitis treatment.

(Additional references 2-16 as listed in the original protocol are summarized and referenced in the document for completeness.)

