Assuming a probability of clinical and endoscopic remission at 8 weeks and sustained without corticosteroid reintroduction or rescue treatment at 54 weeks of 20% in the control group (oral prednisone), a total of 148 patients are needed to detect a $\geq 20\%$ improvement in the therapeutic group (one-tailed test) with a significance level (α) of 0.05 and a power (β) of 0.20, accounting for an estimated 10% dropout rate.

IV) Randomization and Blinding Techniques

After the patient signs the informed consent document approved by the Research Ethics Committee and AEMPS, and meets all inclusion criteria and none of the exclusion criteria, they will be eligible for inclusion in the trial. Patients will be randomized (1:1) into each treatment arm via a computerized system provided by AEG-RedCap. Randomization will be performed in blocks of 4 and stratified by (1) whether the disease is newly diagnosed, and (2) whether the patient has received maintenance treatment with mesalazine at doses > 2 grams/day in the last three months.

This is an open-label study, meaning both the study subjects and investigators will be aware of the assigned treatment. However, blinding will be maintained in the analysis of blood samples for corticosteroid response predictive factors and calprotectin levels in fecal samples, which will be centralized and blinded. The technician conducting the measurement will not know the treatment arm or the clinical response associated with each sample.

V) Treatment Description

The study medication (methylprednisolone for intravenous bolus) will be supplied by the sponsor, while the oral prednisone, calcium supplements, and aminosalicylates will be supplied as per routine clinical practice.

Treatment Groups:

1. **Intravenous Bolus Group:** 0.5 g/day of methylprednisolone administered intravenously for 3 consecutive days, followed by oral prednisone 60 mg/day for 1 week, with a subsequent tapering regimen (decrease by 10 mg weekly until 20 mg, followed by a decrease of 5 mg weekly until complete withdrawal).
2. **Oral Prednisone Group:** 60 mg/day for 1 week, followed by a tapering regimen (decrease by 10 mg weekly until 20 mg, followed by a decrease of 5 mg weekly until complete withdrawal).

In both groups:

- **Concomitant 5-ASA Suppository Treatment:** 1g/day during the first 4 weeks.
- **Calcium and Vitamin D Supplementation:** Calcium 1000 mg/day and Vitamin D 800 IU/day until corticosteroid withdrawal.

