
SARE information will be sent annually, in aggregate form, with a brief analysis of the data provided.

Throughout the study, investigators will be informed of any safety aspects that affect the conduct of the clinical trial or protocol amendments related to safety.

IV) Type and Duration of Follow-up of Subjects After Adverse Events

If a patient experiences any disease or adverse event during the study that, by itself or due to requiring pharmacological treatment, may alter the disposition of any of the study drugs or make its administration unadvisable, the patient will be excluded from the study, and the cause will be detailed. If the adverse reaction is mild or moderate, requires treatment or not, and does not lead to discontinuation of the drug, the reaction will be detailed, and the study will proceed as planned.

Notification

Report on the corresponding data collection form (Annex 5).

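### Two sections give opposite follow-up rules for an event that alters study-drug disposition: one keeps the patient in follow-up, the other removes the patient, whom non-response imputation then counts as a failure

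*Combined protocol and SAP*

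**What the plan says.** Section 5 (Justification), III deals with an event that "requires pharmacological treatment or modifies the study drugs' disposition, the study medication must be withdrawn". In that case "the adverse event will be monitored until resolution and the participant followed up until the end of the study".

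Section 11 (Safety Evaluation), IV, the part on follow-up after adverse events, deals with a disease or event that, by itself or through the drugs it calls for, "may alter the disposition of any of the study drugs or make its administration unadvisable". There the instruction is that "the patient will be excluded from the study, and the cause will be detailed". The next sentence lets a mild or moderate reaction run on when it "requires treatment or not, and does not lead to discontinuation of the drug".

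Three other places decide what follows:

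- Section 7, I: the primary outcome needs steroid-free clinical and endoscopic remission at both week 8 and week 54, with no rescue treatment in between. Rescue includes "restart or increase of the established corticosteroid dose" or starting a colitis treatment other than mesalazine. Stopping the study drug for an adverse event is not listed as rescue.
- Section 12, I: the ITT set holds every randomised patient who was dosed. The PP set keeps patients whose regimen was cut short by an adverse event or treatment failure. Missing primary-outcome data are imputed as non-response.
- Section 7, VII and Section 8, III: serious steroid complications are among the reasons for which a patient may leave the study. A change in drug disposition is not on either list.

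**The concern.** Both rules are written as mandatory, and they part on the one thing that matters for analysis, which is whether the patient is still assessed. A site that follows Section 5 observes the outcome. A site that follows Section 11, where one would naturally look for the rule, does not, and imputation fills the gap with a failure.

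The protocol would then be creating its own missing data. Non-response imputation is a reasonable fallback for losses that cannot be avoided, but here the patient may be willing and able to attend. The time-to-event analyses of relapse, steroid dependency and surgery lose the same follow-up. The loss for safety is small, because Section 11, II still follows known adverse reactions and serious events to resolution, irreversibility or study completion.

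**Working it through.** **Where the two rules overlap.** The triggers are not identical. Section 5 also covers any event needing drug treatment; Section 11 also covers events that make dosing inadvisable. The clear conflict is confined to events that alter study-drug disposition.

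**What happens to such a patient.**

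1. Section 5: drug stopped, visits continue, week 8 and week 54 observed.
2. Section 11: patient leaves. Week 54 is missing. Section 7, VI gives a treatment duration of 8 weeks, so an event during treatment also removes week 8.
3. Section 12: the patient stays in ITT because dosed, and in PP because the regimen ended for an adverse event. The missing outcome becomes a failure in both. Section 11 does not mention imputation; this step follows from reading Sections 7 and 12 together.
4. The result changes only for a patient who would have met the primary outcome. One who fails at week 8 or takes rescue is a failure under either rule.

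**The plan's own figure.** Inputs from Section 7, III: control rate 20%, improvement 20 points, one-sided alpha 0.05, power 80%, 10% dropout, 148 patients. Section 12 confirms 40% as the expected experimental rate. With pooled variance and no continuity correction:

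n per arm = [1.645 × √(2 × 0.30 × 0.70) + 0.842 × √(0.16 + 0.24)]² / 0.20² = (1.066 + 0.532)² / 0.04 ≈ 63.9, so 64.

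Dropout: 64 / 0.9 = 71.1, so 72 per arm and 144 in total. The plan states 148, a difference of 4 (2.7%). I use 148 / 2 = 74 per arm below.

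**Sensitivity of power.** The exclusion shares are assumptions; the documents give none. With imputation, arm rate = planned rate × (1 − exclusion share), if excluded patients would have responded at the full planned rate. Power = Φ{[d√74 − 1.645√(2p̄(1 − p̄))] / √(p₁(1 − p₁) + p₂(1 − p₂))}, where p₁ and p₂ are the two arm rates, d their difference and p̄ their mean.

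| Excluded in each arm, no other losses | Oral v bolus rate | Power |
|---|---|---|
| 0% | 20% v 40% | 85.0% |
| 2.5% | 19.5% v 39% | 83.8% |
| 5% | 19% v 38% | 82.5% |
| 10% | 18% v 36% | 79.9% |

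Worked line for 10%: d√74 = 0.18 × 8.602 = 1.548; 1.645 × √(2 × 0.27 × 0.73) = 1.033; denominator √(0.1476 + 0.2304) = 0.615; (1.548 − 1.033) / 0.615 = 0.84; Φ(0.84) ≈ 0.799.

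Per patient, one bolus exclusion lowers the expected bolus rate by 0.40 / 74 = 0.54 points, and one oral exclusion lowers the oral rate by 0.20 / 74 = 0.27 points. One in each arm therefore costs 0.27 points of the 20-point difference.

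These losses are upper bounds for the stated shares. If excluded patients would have responded at half the planned rate, 10% in each arm gives 19% v 38% and 82.5%. If none would have responded, nothing is lost.

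**The case against.** The strongest reply is that almost no harm can be shown. A patient taken off steroids in mid-flare may well need rescue, or miss remission at week 8, and so fail under either rule. Sections 7, VII and 8, III would let many of these patients leave anyway. The sample size was set "accounting for an estimated 10% dropout rate", and an exclusion under Section 11 is one form of dropout. Section 12 already fixes how such patients are analysed. All of this stands, and it is why the point is minor.

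It could also be said that exclusion merely means coming off the drug. The wording is against that: Section 11, IV speaks of leaving the study, and its next sentence refers separately to stopping the drug. If coming off the drug was meant, the edit below says so at little cost.

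A reader might go further and infer three things that the documents do not support:

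- *A real power deficit.* If other dropouts already used the whole 10% allowance, a further 10% of exclusions per arm would give 16% v 32% and 74.1% power. No section says that the allowance is already spent.
- *Bias against the bolus arm, or inflated type I error.* Excluding 5% of oral and 10% of bolus patients gives 75.3% power. The reverse, with both true rates at 20%, gives a one-sided type I error of 6.8%. Both need unequal exclusions. The rationale in Section 5 hopes for outpatient boluses "without increasing the risk of adverse events", and nothing suggests an excess in the oral arm. Investigators know the allocation and could apply the two rules unevenly, but nothing shows that they would.
- *Patients dropped from the analysis.* Section 12 keeps them in both sets. What is lost is their observation.

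**Conclusion.** The contradiction is in the text and is unresolved for events that alter study-drug disposition. Its consequence is avoidable missing data: an outcome that could have been observed becomes an imputed failure in ITT and PP, and later secondary follow-up is lost.

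The frequency of these events is not given, so the size and direction of any effect on the treatment comparison cannot be derived. Equal exclusions of up to 10% per arm, with no other losses and full planned response, leave power at about 80% or higher. The effect is probably small. The point rests on the conflicting instructions and the ease of correcting them, not on a power deficit. Severity is low.

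**What to change.** In Section 11, IV, replace the exclusion instruction with a statement that *study medication is stopped and the patient stays in the study for every scheduled visit, the week-8 and week-54 assessments included, unless consent is withdrawn*.

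In Section 7, VII and Section 8, III, state that serious steroid complications are a reason to stop study medication while follow-up continues. This edit is needed: such a complication makes dosing inadvisable and so falls under the revised Section 11 rule, yet the lists would still offer it as a reason to leave.

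Leave the drug-stopping trigger in Section 5, III as it is. Rewriting it would change safety conduct, which goes beyond the follow-up conflict. The imputation rule and the analysis sets also need no change.

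The cost is some extra visits, with up to two rectosigmoidoscopies each, for patients who stop drug early. On assumed shares of 2.5% to 10% of 74, that is about 2 to 7 patients per arm. The visits are already in the Section 7, V schedule, and Section 5 already calls for follow-up to study end.
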